We propose that daily locomotor training in the presence of SCES will enable the individual with clinically complete SCI to stand and step independently while bearing full weight. Non-patterned electrical stimulation of the lumbar spinal cord can induce patterned, locomotor-like activity in individuals with clinically complete SCI [1]. Modifying the frequency of stimulation can induce extensor patterns similar to that observed during standing [45]. In addition, when afferent information is also provided there is further modulation of these motor patterns elicited by epidural stimulation [46]. Individuals with a clinically complete spinal cord injury can execute independent steps using a body weight support system on a treadmill (BWST) using manual assistance without epidural stimulation. When combined with SCES, we anticipate the training will be even more successful, enabling prolonged periods of independent stepping and standing. Although there will not be a separate control group studied simultaneously, historical controls will consist of the best stepping and standing performance that have been observed previously in our laboratory in individuals that have a clinically complete SCI. Performance beyond this threshold by any individual treated with both epidural stimulation and training will be interpreted as a significantly better intervention than training alone.

Future studies will eventually focus on development and implementation of the more advanced multi-electrode array technique that will provide functionally-adaptive site-specific stimulation. The adaptive stimulation strategy proposed here takes advantage of capabilities of our new array design that are not possible using either conventional or commercially available electrode arrays. Our future arrays will provide two key benefits:

- Our electrode arrays cover a larger area than commercially available arrays, extending from the midthoracic to the sacral extents of the spinal cord. It is possible that the optimal stimulation sites for facilitating stepping versus standing may be spatially distinct on the spinal cord. If this is the case, conventional arrays are less likely to be able to recover both stepping and standing in the same patient.

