These individuals will not be concurrently enrolled in any other experimental studies unless approved by the principal investigator. Each research participant will be given a coded identification number to designate all evaluations. We will retain the data for reporting to granting agencies even when the individual is not eligible for the study. This data will be stored by the coded identification number without information identifying the individual.

We will evaluate the research participants for: 1) functional neurophysiological assessment (FNPA); 2) somatosensory evoked potentials (SEP); 3) sympathetic skin responses (SSR); 4) efferent motor activity during standing; 5) efferent motor activity during stepping; 6) reflexes during supine, prone, sitting and standing; 7) bladder function; and 8) cardiovascular function. Each of these measurements will take between 1 and 4 hours. The FNPA, SEP and SSR will be performed while the research participant is lying supine on a mat. The efferent motor assessments will be performed in the body weight support treadmill with the assistance of trainers at the hip and at each leg.

We will assess metabolic parameters, inflammatory markers, complete blood count, bone density and health markers, blood glucose control and drug toxicity panel. A trained

technician will draw a venous blood sample. Participants may undergo a 12-hour fast the night before, including no food or drink including alcohol or caffeine (water is permitted). A comprehensive drug screen by urinalysis will be done to assess the use of illicit drugs. These blood and urine analyses may be repeated periodically throughout the course of the study. A blood sample will be stored for batch processing at the end of the study (for participants that complete the screening process).

After completion of these evaluations, participants will undergo 80 sessions of step/stand training. We will repeat experiments after the completion of the 80 training sessions to quantify that no motor pattern changes are achievable with locomotor training alone. Drs. [name], [name] and [name] will meet to discuss the results of the preliminary testing and evaluate if the participant is eligible for surgical implantation for SCES.

FULL ENROLLMENT: Surgery + Epidural Stimulation + Training (2nd consent)

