If after evaluating the results, the study investigators determine that the participant is an appropriate candidate for surgery and epidural stimulation, the participants will be asked to sign an additional consent form. The surgical and epidural stimulation informed consent will be written in at a 8th-grade language level and will contain information on the surgery and all experiments to be performed as well as contact information should the research participant or his/her associates have any further questions. The original signed informed consent and two copies will be kept in [name] office.

The surgery will be performed at University Hospital to insert the epidural stimulating electrodes. The lead wires will be tunneled subcutaneously to exit 5 centimeters from the incision site. The implantable neurostimulator will be internalized and the connecting wires for the implanted electrodes will be tunneled under the skin and connected with the battery generator that will be placed in the abdominal area. We will repeat the experiments beginning at least 10 days after the surgery both with and without stimulation for 10 – 14 days. During the first two weeks after the surgery, the research participants may be hospitalized at Frazier Rehab Institute to monitor the incision site. We will also identify appropriate stimulation parameters for inducing stepping and standing in combination with manual assistance using body weight support on a treadmill (BWST).

Following discharge from inpatient or recovering at home the individuals will be seen in our lab on a daily basis for testing and locomotor training. We will evaluate the combination of epidural stimulation with manual step/stand training. This stage will be conducted over six-eight months. During training, the patients will be provided with epidural stimulation using the parameters defined in Stage 1. Testing may be performed weekly. The blood samples for metabolic parameters may be repeated prior to and after each training period. A blood sample will be frozen and stored in the laboratory for batch analysis for inflammatory markers, metabolic parameters, and markers for bone density.

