Stage 1A: Standing and stepping interventions

FULL ENROLLMENT CONSENT:

Stage 1B: Surgical Procedure

Stage 1C: Stimulation procedures and standing and stepping interventions

Stage 2A: Stimulation procedures and standing and stepping assessments

Stage 2B: Adaptive Multielectrode Epidural Stimulation and Locomotor Training

Stage 1A: Standing and stepping interventions

Prior to the initial surgery the participant will undergo 80 sessions of step/stand training (screening). We will evaluate the research participants with the following experiments: 1) functional neurophysiological assessment (FNPA); 2) somatosensory evoked potentials (SEP); 3) sympathetic skin responses (SSR); 4) efferent motor activity during standing; 5) efferent motor activity during stepping; 6) reflexes during supine, prone, sitting and standing before the initiation of training; 7) bladder function; 8) cardiovascular function; 9) MRI Scan; 10) Quality of life questionnaires. Each of these measurements will take between 1 and 4 hours. We will repeat these measurements at the end of the initial 80 training sessions. Participants will undergo laboratory tests to assess and reduce the risk of infectious diseases prior to surgery.

Protection against Infectious Diseases: Several lab tests (see table below) will be performed to assess the risk of infection prior to surgical implantation based on the recommendation from the Infection Prevention and Control Department (ULH) and Division of Infectious Diseases, Dept. of Medicine (UofL). [name] will oversee treatment for any positive urine culture and infections in consultation with the Division of Infectious Diseases Department.

Test	Purpose	When
Nasal swab for MRSA	To determine if colonized to decolonize and use vancomycin as pre-operative antibiotics	Approximately 4 weeks prior to scheduled surgery to allow for time for treatment, re-test + treatment and final re-test.
Peri-rectal swab for MDRO Gram-negatives	To determine if colonized and, based on organism, consider decolonization and adjustment of pre-operative antibiotics	
urinalysis urine culture	To identify infection for clearance prior to procedure	Within 30 days of scheduled surgery; may need to be repeated closer to surgery date
C-reactive protein (CRP)	To obtain for baseline measure	
Erythrocyte sedimentation rate (ESR)		
Procalcitonin		
Prealbumin/Transthyretin	To verify appropriate status for procedure	
Albumin (included in CMP)		
25-Hydroxy Vitamin D		
CBC with differential		

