Stage 1C: Stimulation procedures and standing and stepping interventions

We may repeat experiments that were performed pre-surgery beginning 2 weeks after the surgery both with and without stimulation for 10 – 14 days. During the two weeks after the surgery, the research participants may be hospitalized at Frazier Rehab Institute to monitor the incision site.

Optimal configurations will also be tested for bladder and cardiovascular function. A specific stimulation parameter may be used to assess the influence of epidural stimulation on bladder function and/or cardiovascular function. In the case of bladder function, following its assessment with stimulation the bladder will be filled with saline solution a second time after a 5 minute break. The optimal stimulation configuration for bladder will be used and the pressure will be recorded. The individual will be asked to attempt to empty his/her bladder when the stimulation is ongoing. Pressure will also be recorded when the bladder is relieved. This test will take approximately 60 minutes.

Similarly the cardiovascular function might be assessed without and with stimulation. The orthostatic stress test (sit up test) might be repeated with optimal stimulation for cardiovascular control. The butterfly catheter will remain in place from the initial non stimulation test and blood samples will be obtained to same time points to assess if any changes in

We will also identify appropriate stimulation parameters for inducing voluntary activity and stepping and standing in combination with manual assistance using body weight support on a treadmill (BWST) or overground. Each of the sixteen electrodes will be independently stimulated using subthreshold, tonic, non-patterned epidural stimulation applied at frequencies of 5-50 Hz, and amplitudes of 1-10 V. The specific stimulation parameters will be optimized for each individual to achieve the best motor performance for each task. We may monitor continuous blood pressure, breathing rate and temperature using external sensors pasted over the skins during training sessions or experiments.

Stage 2A: Stimulation procedures and standing and stepping assessments

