Following post-surgery experiments, training will be conducted 5 times per week for 160 sessions on an outpatient basis. In Stage 2 the individuals will be seen in our laboratory on a daily basis for testing and training. After the initial 20 sessions of training, they might be asked to come train twice a day (stand and step on the same day) with a 2-4 hour resting period in between. We will evaluate the combination of epidural stimulation with manual step (locomotor) training. This stage will be conducted over four to eight months. Periodically, blood and urine samples may be collected, processed for testing as described above, and stored for batch testing at the end of the study period.

During training, the patients will be provided with epidural stimulation using the parameters defined in Stage 1.

In certain cases, the physician, [name], might recommend a specific training change or limit on sessions to mitigate risk for research participant. Any special considerations are specified in the addendum section.

The participants may be evaluated weekly for 1) efferent motor activity during standing and stepping and 2) reflexes during supine, prone, sitting and standing, as described above.

Home Training: Following the determination of optimal parameters for standing or voluntary activity, the participant might be given a Patient Programmer (Medtronic Model 37743) to translate weight bearing and stand training and/or voluntary movement with stimulation to the home environment and perform additional training. The programmer will be optimally programmed by the research team in such a way to restrict configuration changes by research participant. A pre-determined range of optimal voltages will be accessible by the research participants. A very specific protocol for stimulation and training will be given by the research team and the participant will be required to complete a training log. The research team will collect the home training log from the participant once a week and evaluate the need for changes to the home-based training protocol.

Stage 2B: Adaptive Multielectrode Epidural Stimulation and Locomotor Training

Stage 2 will evaluate the combination of our adaptive epidural stimulation strategy with manual step (locomotor) training. During training, the participants will be provided with ES using the parameters determined using the computation learning method in Phase 1.

Experimental materials.

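### Gains made during the 160 stimulated sessions cannot be credited to stimulation rather than further training or time: no stimulation-off motor test is fixed after them, and the historical controls' training dose is not stated

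*Protocol*

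**What the plan says.** **The decision rule.** Section A of the protocol has no concurrent control. The threshold is the best standing and stepping seen earlier in the same laboratory in people with clinically complete injury. Performance above it by any individual given stimulation plus training "will be interpreted as a significantly better intervention than training alone". The last paragraph of section G repeats that the best earlier training-only results set the criterion for success.

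**Training alone.** Participants have 80 sessions before surgery. Section G, Stage 1A: "We will repeat these measurements at the end of the initial 80 training sessions". Section D (Screening) gives the purpose of that retest: "to quantify that no motor pattern changes are achievable with locomotor training alone".

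**After surgery, before the stimulated block.** Section D (Full Enrollment): "We will repeat the experiments beginning at least 10 days after the surgery both with and without stimulation". Section G, Stage 1C: "We may repeat experiments that were performed pre-surgery beginning 2 weeks after the surgery both with and without stimulation".

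**The stimulated block.** Section G, Stage 2A: "training will be conducted 5 times per week for 160 sessions on an outpatient basis", with stimulation on during training. Sections D and G both have participants attending daily for testing as well as training. On the content of that testing, section D says "Testing may be performed weekly" and Stage 2A says "The participants may be evaluated weekly for 1) efferent motor activity during standing and stepping". Neither names a stimulation-off condition or an assessment at the end of the block.

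**The concern.** The section A rule compares two programmes, training with stimulation and training without it. To credit a difference to stimulation, the two sides must have comparable training, or stimulation must be switched off at the point where the gain is seen. The protocol secures neither.

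What is at stake is the reading of any gain that appears during the 160 sessions. The protocol itself treats training alone as able to produce something: section A describes independent treadmill steps with manual assistance, and brief full-weight standing after weeks of stand training, both without stimulation. Further training is therefore a live explanation. With ten participants and no concurrent control, a comparison that is not made at the end of the block cannot be recovered afterwards.

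The claim attached to the session-80 retest has the same weakness. A single retest can show what had changed by session 80; it cannot show what training alone could ever achieve.

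**Working it through.** The protocol gives no sample-size, power or effect figure for this comparison, so there is none to reproduce. The check sets out the motor assessments in order and asks what each can separate.

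**Inputs.** 80 sessions without stimulation (section G, Stage 1A); 160 sessions with stimulation (Stage 2A). Stage 2A starts after the post-surgery experiments, which fixes the order.

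| Motor assessment | Planned sessions so far | Stimulation | Status |
|---|---|---|---|
| Before training (sections D, G Stage 1A) | 0 | none | firm |
| Training-alone retest (sections D, G Stage 1A) | 80 | none | firm |
| Post-surgery on/off test (sections D, G Stage 1C) | 80 | on and off | *will* in D, *may* in 1C |
| During the stimulated block (sections D, G Stage 2A) | 80 to 240 | not stated | attendance for testing firm; weekly evaluation *may* |
| End of the stimulated block | 240 | not stated | no time point fixed |

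**Arithmetic.**
- Cumulative planned sessions: 80 + 160 = 240. Of these, 160 are the combination and 80 are training alone.
- Planned sessions after the last specified stimulation-off motor test: 160/240 = 2/3.

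These are counted sessions. Section D counts a session only if progression criteria are met, and Stage 2A allows added home training, so exposure may be higher.

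**What can be separated.** As a simple additive description, the change from the session-80 retest to a stimulated test at the end of the block is:

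change = (a) immediate effect of having stimulation on + (b) lasting effect of having trained with stimulation + (c) effect of 160 more sessions of training as such + (d) time.

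- The post-surgery on/off test, if done, estimates (a) before the 160 sessions. It says nothing about (b), (c) or (d).
- A stimulated-only test at the end gives the sum of all four.
- An on/off test at the end would isolate (a) at that time. The off-condition change since the post-surgery test would give (b) + (c) + (d) together, still undivided.

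**The historical side.** Section A and the last paragraph of section G give no number of controls, no sessions delivered and no session count for the comparison. The number matters because the best of a few is a lower bar than the best of many. The dose matters because a best result after few sessions is not comparable with performance after 240. No ratio of training dose to the controls can be formed.

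**The case against.** **Proof of principle.** Section j says that no statistical comparison will be made and that the study has no statistical power. That is fair, and no test or power calculation is asked for. But it does not license the section A rule, which draws a comparative conclusion from a single individual.

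**The run-in and chronic injury.** Injury must be non-progressive and at least one year old (section F), and the 80-session results inform the surgery decision (section D). Both make time and further training less likely explanations. Neither shows that performance without stimulation would stay flat through the next 160 sessions.

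**A demanding bar.** The threshold is the laboratory's best result, not an average. This stands as far as it goes, but a best result at an unstated dose from an unstated number of people cannot be placed against performance after 240 sessions.

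**Readings that go too far.**
- A reader might infer that the combination runs to 240 sessions. It does not: 240 is cumulative and the combination is 160.
- A reader might take 240 against 80, a factor of three, as the dose imbalance in the section A comparison. That factor describes the participant's own session-80 retest; section A compares with historical controls whose dose is unknown.
- A reader might conclude that no testing is planned during the stimulated block. Sections D and G say that participants will attend for testing. What is missing is a fixed off condition and an end-of-block time point.
- A reader might see conflicting start times for the post-surgery test. Two weeks satisfies a minimum of 10 days; only *will* against *may* conflicts.
- A reader might expect participants to finish with no on/off test. Stage 1C's wording permits that, but section D is firm and Stage 2A presupposes post-surgery experiments.
- Section A's remark that training may progressively alter spinal networks might be cited as evidence of late gains from training alone. It is an argument about migrating stimulation sites.

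**Conclusion.** The point holds in limited form. The design can support a descriptive statement about the combined programme at its own training dose. If the on/off test is done, it can also support a statement about the immediate effect of stimulation soon after surgery. It cannot support the section A attribution for gains that emerge during the 160 stimulated sessions.

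The only size the document allows is structural: 160 of 240 planned sessions come after the last specified stimulation-off motor test. The share of any gain due to further training or time cannot be computed. Nothing here shows that training or time would in fact explain a gain, only that the plan does not separate them.

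This assumes that planned counts approximate delivered sessions and that no stimulation-off motor test after the block is specified outside this protocol. The change should be made: it is cheap and alters what the study can conclude.

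**What to change.** 1. Reconcile section D (Full Enrollment) with section G, Stage 1C, so that the post-surgery on/off motor assessment is firm in both.
2. Fix one on/off motor assessment at the end of the 160 sessions, within the testing already permitted. Report on-minus-off as the immediate stimulation effect, and state that this does not separate training from time.
3. State the number of historical controls and the sessions they received, and compare at similar session counts where possible. Otherwise limit section A and the last paragraph of section G to a descriptive conclusion about the combined programme at its own training dose, without attributing the gain to stimulation.
4. In section D (Screening), replace the claim that no change is achievable with training alone by a statement of whether change was seen after 80 sessions.

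**Cost.** Items 1 and 4 are wording. Item 3 is wording plus a summary of the laboratory's earlier data, or wording alone if the narrower conclusion is chosen. Item 2 means a somewhat longer test visit or one extra visit. The result may attribute less to stimulation than section A now would. On-minus-off may also understate stimulation's full contribution, because any lasting carry-over appears in both conditions; the report should say so.

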We will acquire lower extremity and trunk muscles surface EMG activity and kinematics bilaterally during all experimental conditions. We will also use fine-wire EMG to acquire activity from the ilio-psoas, extensor hallicus longus, extensor digitorum longus and other deep muscles muscle. We will also record individual limb loading and level of BWS during standing and stepping conditions. We may acquire continuous blood pressure with a finger cuff, breathing rate using an elastic band place loosely around their chest and temperature with 1-3 small sensors taped over their skin above and below their injury level.

Locomotor Training Intervention.

Individuals with SCI will participate in 80 sessions of weight bearing step-training (n=10) for approximately 16 - 20 weeks (60-90 minutes/session, 3-5 sessions/week) during which the individuals may be placed on the treadmill in an upright position and suspended by an overhead pulley (Innoventor, St. Louis, MO) in a harness (Robertson, Hendersen, NV). During stepping using BWST and manual assistance the maximum load will be used that avoids knee-buckling and trunk collapse [64]. A trainer positioned behind the research participant will aid in pelvis and trunk stabilization, as well as weight shifting and hip rotation, and trainers positioned at each limb will provide manual assistance using a customized technique that facilitates knee extension during stance (by manually

stimulating the patellar and Achilles' tendons) and knee flexion and toe clearance during swing (by manually stimulating the hamstrings and tibialis anterior tendons). Trainers provide assistance only when needed. Individuals will step at a normal walking speed for their height and age (0.89 m/s – 1.34 m/s) and at the maximum body weight allowed with minimal force needed by the trainers to assist during stance (4, 25). Body weight support will be continuously reduced over the course of the 80 sessions as the individuals increase their ability to bear weight on the legs during stepping. Step training sessions might progress to the overground environment when appropriate.

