We will collect electromyography (EMG), joint angle, and footswitch data at 1000 Hz using a 24-channel hard-wired analog to digital board and a custom written Labview software acquisition program (National Instruments, Austin, TX) during stepping using BWST or overground and manual assistance. EMG data will be sampled from 0.1 to 1 kHz and AC coupled into a differential amplifier (Konigsberg Instruments, Pasadena, CA). Following standard skin preparation, bipolar surface EMG electrodes with a fixed distance between the electrodes will be placed on the soleus, medial gastrocnemius, tibialis anterior, medial hamstrings, adductor, vastus lateralis, and rectus femoris bilaterally. Limb kinematics will be digitally acquired a passive marker high speed motion capture system (Motion Analysis, Santa Rosa, CA). Individual limb loads will be measured with shoe-insole pressure sensors (FSCAN, Tekscan, Boston). Data will be processed and synchronized using Labview software (National Instruments, Austin, TX) customized by our laboratory. EMG data will be full wave rectified and filtered using a 4th order bandpass Butterworth filter (40 Hz - 500 Hz). Mean EMG represents the relative number and frequencies of the motor units recruited per burst. Integrated EMG assesses the total EMG activity generated per step. EMG mean and integrated amplitudes from each muscle will be compared before and after locomotor training. Co-activation values of flexors and extensors will be calculated. The degree of coordination in the stepping-related oscillations of lower limb segments will be assessed through principal component analysis. Quantitative measurements and statistical testing have been described in detail in previous publications listed above.

Heart rate will be monitored using a digit pulse oximeter placed on the index finger of the research participant during training sessions and experiments.

Next analytical approaches will be utilized in these studies:

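### The before-after comparison of per-muscle surface-EMG amplitude has no visible same-session reference, so electrode re-application and tissue change can mimic or hide a motor change

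*Protocol*

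**What the plan says.** Section G, Locomotor Training Intervention, sets out the EMG chain. After standard skin preparation, "bipolar surface EMG electrodes with a fixed distance between the electrodes will be placed on the soleus" and on six further muscles, all bilaterally, which makes 14 channels. The signal is rectified and band-pass filtered at 40-500 Hz. The plan then states that "EMG mean and integrated amplitudes from each muscle will be compared before and after locomotor training", and it gives amplitude a physiological meaning: "Mean EMG represents the relative number and frequencies of the motor units recruited per burst". The EMG burst cycle analysis item repeats that meaning in softer terms, as an interpretation that may be made.

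The timing comes from three places. Section G gives the pre-surgery block as 80 sessions over roughly 16-20 weeks. Stage 1A says "We will repeat these measurements at the end of the initial 80 training sessions". Stage 2A says that "training will be conducted 5 times per week for 160 sessions on an outpatient basis".

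One use of the pre-surgery comparison is stated in Section D (Screening): the experiments are repeated "to quantify that no motor pattern changes are achievable with locomotor training alone", after which the investigators discuss eligibility for implantation.

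**The concern.** A surface-EMG amplitude is the muscle's activity multiplied by a recording gain. That gain depends on where the electrodes sit, on the skin contact and on the tissue beneath. Skin preparation and fixed spacing control part of it. They do not fix the site on the muscle, and they do not hold the tissue constant.

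Over an interval of months the electrodes must come off and go back on. Section D (Locomotor Training) expects muscle to become stronger early in training, and it allows electrode placement to be changed if the skin is irritated. So the gain has reason to differ between the two recordings.

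All steps in a session share the same gain, so averaging more steps does not remove the error. If amplitude is then read as motor-unit recruitment, a gain shift can be taken for a training effect or can cancel a real one. At stake are the mechanistic EMG findings and the EMG part of the check that training alone changes no motor pattern.

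**Working it through.** **1. Is there an amplitude reference anywhere in the text?** The candidate steps in Section G are these.
- Linear envelopes: averages are normalised to burst or cycle duration. This rescales time, not amplitude.
- EMG burst cycle analysis: a threshold of 3 SD above baseline noise marks burst onset and end. It does not scale amplitude.
- Voluntary response index: vectors are divided by their magnitude across muscles. This applies to that index only, and it cancels only a gain shared by all channels.

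None of these applies a same-session reference to the mean or integrated amplitudes.

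**2. How far apart are the recordings?**
- Pre-surgery block: 80 sessions / 5 per week = 16 weeks, and 80 / 4 = 20 weeks, which reproduces the stated 16-20 weeks. At the lowest stated rate of 3 per week, 80 / 3 = 26.7 weeks.
- Post-surgery block: 160 / 5 = 32 weeks.

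**3. What can gain alone do?** Write recorded amplitude = g × A, with g the gain of one electrode application and A the true activity. Then after/before = (g2/g1) × (A2/A1). With no true change, A2/A1 = 1. If log g has SD s and the two applications are independent, the log ratio has SD √2·s and the 95% range is exp(±1.96·√2·s). The chance of an apparent shift of 1.5-fold or more in either direction is 2·[1 − Φ(ln 1.5 / (√2·s))], with ln 1.5 = 0.405.

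The protocol gives no value for s. The values below are an **assumption**, shown as a range.

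| s (log scale) | √2·s | 95% range of ratio | Chance of ≥1.5-fold shift, one channel | Expected number of 14 channels |
|---|---|---|---|---|
| 0.10 | 0.141 | 0.76-1.32 | 0.4% | 0.06 |
| 0.20 | 0.283 | 0.57-1.74 | 15% | 2.1 |
| 0.30 | 0.424 | 0.44-2.30 | 34% | 4.7 |
| 0.40 | 0.566 | 0.33-3.03 | 47% | 6.6 |

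The last column is 14 × the chance for one channel.

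**4. Which measures escape?**
- Two phases of the step cycle in the same channel and recording: (g·A_phase1)/(g·A_phase2). The gain cancels.
- Two muscles in one recording: (g_a·A_a)/(g_b·A_b) leaves g_a/g_b. With independent gains, its before-after change involves four gains and has log SD √4·s = 2s, wider than the √2·s of a single channel.
- Stimulation on versus off through the same electrodes on the same day: the application is shared, so the gain cancels.
- Burst timing depends on gain only through the detection threshold, so it is less exposed but not immune. Kinematics do not use EMG gain.

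**The case against.** The strongest objection is that the point rests on silence. The protocol never calls the amplitudes raw or absolute. It refers to earlier publications for its quantitative methods, and normalisation is the sort of detail often kept in a laboratory procedure. Part of this stands: a reference step may exist in a source not at hand. But the protocol does spell out its processing chain and then commits to the before-after amplitude comparison. Followed as written, that comparison carries the gain, and a general pointer does not put a reference step into the plan.

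The size is assumed. At s = 0.10 a 1.5-fold shift in a given channel is rare (0.4%), so the problem could be small. That stands in full.

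The stimulated phase may include weekly testing (Section D and Stage 2A), so there may be more than two applications, and independent placement error would average down over them. That also stands for that phase, with two limits: the testing is optional, and a steady tissue change does not average out.

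Many gain-robust measures are already planned: burst timing, coordination by principal components, kinematics, and post-surgery experiments with and without stimulation. This is correct. It is why the repair is easy, but it does not repair the amplitude sentence.

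A reader might infer that the trial's conclusion is undermined. The documents do not support that. Success is judged on stepping and standing performance against the best historical results with training alone (Section A and the end of Section G), and Section j plans no statistical comparison. A reader might also infer that the implant decision turns on amplitude in single muscles. It does not: Section D and Stage 1A list many tests, and none makes a single-muscle amplitude decisive.

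**Conclusion.** The point holds in a limited form. The plan compares each muscle's mean and integrated amplitude across electrode applications about 16-20 or 32 weeks apart and reads mean amplitude as recruitment. No visible step separates motor change from gain change. This affects the mechanistic EMG reading and the EMG part of the pre-implant check, and nothing beyond them.

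That the confounding exists follows from the text. Its size does not: the 95% range of 0.76-1.32 up to 0.33-3.03 rests on an assumed gain SD of 10-40% on the log scale, independent between applications. It would be too strong to say that large false changes are expected, or that any visible change will be taken as a training effect. The point is a cheap improvement to one stated analysis.

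**What to change.** Amend the amplitude sentence in Section G (Locomotor Training Intervention) as follows.
- Interpret unscaled mean and integrated amplitude only within one electrode application, for example stimulation on versus off on the same day.
- Base before-after comparisons on burst timing, coordination and kinematics, or on amplitude ratios within the same channel and recording, for example between phases of the step cycle. Do not rely on ratios between muscles, because they cancel only shared gain.
- If a same-day reference through the same electrodes is already recorded for a muscle, before-after amplitude divided by that reference may be reported. Otherwise report before-after amplitude as descriptive only.

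A maximal direct motor response would be one such reference, but the protocol does not show that the reflex tests include it or that it can be obtained in all 14 muscles. Requiring it would add a procedure, so it is not part of this fix.

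Cost: a change of wording and some analysis code, with no new visits, recordings or participants. The loss is that unscaled before-after amplitude can no longer be offered as evidence of a training effect.
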